6.1.3 Endpoints of the study

6.1.3.1 Primary endpoint

Time period in days from index use of Suprasorb[®] CNP endo to release for oral food intake (in upper GI tract use) or endoscopic release for stoma relocation (in lower GI tract use).

In case of lower GI tract use and no stoma present, time period to release for oral food intake is the relevant endpoint.

6.1.3.2 Secondary endpoints

- 1. Number of SAEs related to defect treatment within total observation period.
- 2. Number of nights in hospital for therapy of index defect.
- 3. Number of nights at the ICU during hospital stay for therapy of index defect.

Nights at an intermediate care unit (IMC) will not count for this secondary endpoint.

SAEs will be adjudicated by an independent Clinical Event Committee (CEC) according to standard definitions. Wherever reasonable, endpoints will be normalised to one year of follow-up to adapt results to varying follow-up periods.

"Index defect" describes for each study patient the defect(s) which lead to the clinical indication of treatment with Suprasorb[®] CNP endo system according to IFU and medical guidelines as defined in 6.3.1.

"Index therapy" describes for each study patient the first use of Suprasorb[®] CNP endo for therapy of the index defect.

6.1.4 Methods and timing for assessing, recording, and analysing variables

Only data which can be obtained from routine clinical care files of the patients will be recorded. Data of routine clinical care visit after study enrolment will be reported in the e-CRF. Data will be derived from clinical records and findings, radiological assessments, observations or other sources (e.g. hospital records, clinical and office charts, electronic patient records, laboratory notes).

Within this observational study timing of measures and clinical data to be reported are determined by routine clinical care in line with applicable medical guidelines and local policies. The study protocol just defines some procedural recommendations.

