6.3.6 Expected duration of each subject's participation

The mean follow-up period (from date of enrolment to end of follow-up) of all patients is expected to be about 3 months.

6.3.7 Number of subjects required to be included in the study

As discussed in 3.2, the evidence for the different treatment options is very limited. Especially the patient populations, e.g. regarding underlying diseases, as well as the processes in the therapy are very different in the individual studies published. Therefore a reasonable sample size calculation is not possible at the moment. Thus, an interim analysis with sample size re-calculation is planned.

The best evidence for an **initial sample size calculation** is provided by data of the study by Wasmann et al. [29], a cohort study including 334 patients with ileal defects, where EVAC therapy was compared to conventional management of defect treatment. The median time to stoma relocation was estimated as 4 months in the EVAC group (interquartile range 3 to 6 months) versus 4 months (3 to 13 months) in the conventional management group. Therefore, the proportion of patients with stoma relocation after 6 months is known as 75% in the EVAC group. Assuming a constant increasing proportion in the conventional management group from 4 to 13 months with 2.8% per month, a proportion of 56% stoma relocations after 6 months is expected for the conventional group. Even if the follow-up is set to 3 months in this study, sample size calculation can be based on 6 months results.

Sample size calculation was performed with PASS 16.0.3 using a two-sided, one-sample log rank test. A group sequential design with the alpha spending function of O'Brien-Fleming results in a two-sided type one error of 4.92% for the final analysis. A sample size of 99 analysable subjects achieves 80% power to detect shorter time to release for food intake or endoscopic release for stoma relocation (assuming a proportion of relocated stoma of 75% after 6 months in the EVAC group when the proportion in the historic control group is 56%). The expected number of events during the study with 3 months of follow-up is 13. It is assumed that the survival time distributions of both groups are approximated reasonable well by the Weibull distribution with a shape parameter of 1.00. To account for treatment switching and early drop-outs of 10%, 110 analysable patients will be enrolled.

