6.5 Monitoring plan

No routine onsite monitoring is initially planned within this non-interventional, observational study. Since only observation of routine clinical care without any protocol-defined interventions will be performed, the safety and well-being of study patients is the scope of routine clinical care. Thus, onsite monitoring could be justified for double-check of completeness and quality of data, only. Data quality will primarily be controlled by means of statistical checks on data available for all study sites allowing to detect outliers, extremes and deviation in distribution of data. In case of suspicious findings, on-site visits in corresponding sites might be performed.

7. Statistical considerations

In this observational study the time period from index therapy to release for oral food intake (in upper GI tract use) or endoscopic release for stoma relocation (in lower GI tract use) will be compared to published historic controls. For this, the time period is compared to published data of other EVAC and conventionally managed therapy, especially data from Wasmann et al. [29]. In addition, after half of the patients with complete follow-up, an interim analysis will be performed and sample size will be recalculated. It is expected that until then the results of a randomized clinical trial comparing an EVAC therapy to standard minimally invasive oesophagectomy (refer to NCT04162860 and [22]) will be available for adaptation of assumed confidence intervals and sample size (see 6.3.7). The hypothesis of superiority against conventionally managed therapy will be tested confirmatory.

For primary analysis a one-sample log-rank test will be used, comparing the observed number of events to the expected number of events of the control groups. The two-sided type-one error is 0.54% for the interim analysis and 4.92% for the final analysis.

Data from all study sites will be pooled for analysis. Standard statistical methods will be used to analyse all data. Continuous variables will be summarized using the number of observations, mean, median, standard deviation, minimum and maximum values. Categorical variables will be summarized using the number of observations and percentages.

A separate Statistical Analysis Plan will be prepared prior to the start of data analysis, detailing the statistical analyses methods that will be used.

8. Data management

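### Lower GI stoma patients reach the primary event at endoscopic release, but the only control figures are for completed stoma relocation, so the comparison leans towards the device

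*Protocol*

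**What the plan says.** Section 6.1.3.1 defines the primary endpoint as the time in days from index use of the device to release for oral intake (upper GI) or "endoscopic release for stoma relocation (in lower GI tract use"). Section 5.2.1 uses the same milestones to define wound healing. Lower GI patients without a stoma have a different event: "In case of lower GI tract use and no stoma present, time period to release for oral food intake is the relevant endpoint".

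Section 6.3.7 takes its planning figures from cohort [29], and those figures describe the relocation: "The median time to stoma relocation was estimated as 4 months in the EVAC group". For the controls, "a proportion of 56% stoma relocations after 6 months is expected for the conventional group". The sample size is then stated for a shorter time to food or endoscopic release, while "assuming a proportion of relocated stoma of 75% after 6 months in the EVAC group when the proportion in the historic control group is 56" per cent.

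Section 7 compares the study with published data, naming [29] in particular. It plans a one-sample log-rank test "comparing the observed number of events to the expected number of events of the control groups" and calls the superiority test confirmatory.

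Section 6.4.4 lists time to endoscopic release among the documented outcomes. The date of the relocation is not a listed item there or among the follow-up items in section 6.4.5.

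**The concern.** Release is the clearance for an operation; a relocated stoma is the operation done. Planning, waiting time, recovery or other treatment can lie between them. A released patient counts as an event in the study even if relocation comes much later or never, whereas a patient behind the control figures counts only once relocated.

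The difference has one direction. Release for relocation may coincide with relocation but cannot follow it, so observed events are moved earlier against an expected count built on the later milestone. A device that left the time to relocation unchanged would still tend to show more events than expected. This bears on the primary hypothesis in section 5.2.3, and section 6.3 plans for about half of the patients to be lower GI.

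**Working it through.** **Inputs from the protocol.** Conventional management: median 4 months, upper quartile 13 months (6.3.7). Weibull shape 1.00, 3 months of follow-up, 99 analysable and 110 enrolled (6.3.7). Two-sided level 4.92% at the final analysis (7). Upper and lower GI about equal (6.3). **Assumed, because no document gives it:** the lag d from release to relocation, 0 to 8 weeks.

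**1. The plan's control figure.** From 50% at 4 months to 75% at 13 months is 25/9 = 2.8 points per month, so 50 + 2 × 2.8 = 55.6, or 56%. The figure is reproduced. It comes from the median and upper quartile of time to relocation, so it is a proportion relocated.

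**2. The plan's sample size.** A standard one-sample log-rank formula (exponential, 3 months per patient, 80% power) returns 98.8 patients and 13.3 events, matching 99 and 13, only if 56% and 75% are entered as event-free proportions. Read as proportions relocated, as the text words them, they give 61 patients, and 49.5 events among 99. That is a separate matter. The mismatch of events does not enter this formula; it affects the false-positive rate.

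**3. Expected shift with no device effect.** Control hazard λ = −ln(0.44)/6 = 0.1368 per month. Relocation time T follows the control curve, and release is counted at T − d (day 0 if negative). Per patient over 3 months:

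- observed events: 1 − exp(−λ(3 + d))
- expected events: exp(−λd) × (1 − exp(−3λ))

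At d = 0 both are 0.337. At 4 weeks (0.923 months) they are 0.415 and 0.297. At 8 weeks (1.846 months) they are 0.485 and 0.262.

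Take 55 stoma patients plus 55 others exactly at the control rate (18.5 observed, 18.5 expected):

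- 4 weeks: O = 22.8 + 18.5 = 41.4 and E = 16.3 + 18.5 = 34.8 (sums from unrounded values), so (O − E)/√E is about 1.11
- 8 weeks: O = 26.7 + 18.5 = 45.2 and E = 14.4 + 18.5 = 32.9, so about 2.14

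The critical value is 1.967.

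**4. False-superiority rate** (simulation, 40,000 runs, Z = (O − E)/√E):

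| Lag | Pooled test, 55 of 110 affected |
|---|---|
| 0 weeks | 3% |
| 1 week | 6% |
| 2 weeks | 10% |
| 4 weeks | 22% |
| 8 weeks | 55% |

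With 99 patients instead of 110, the values at 4 and 8 weeks are about 21% and 52%. If the 76.4% diverted share that section 3.2 cites from a meta-analysis applied here, 0.764 × 55 = 42 patients would be affected, and the rates would be about 15% and 38%.

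**5. Data items.** Section 6.4.5 records other treatment at follow-up, but the visit table limits this to on-site visits. A relocation date therefore cannot be relied on to be in the database.

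**The case against.** Several points on the other side stand.

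- **The lag is unknown.** At 0 to 1 week the pooled rate is 3% to 6%, close to nominal. The mismatch is certain; its size is not.
- **Other controls are possible.** Section 6.3.7 uses [29] for an initial calculation and admits that a reasonable one is not yet possible. Section 7 names [29] as a main source, not the only one, and speaks of control groups in the plural. The analysis plan, not shown, may fix another reference. Still, [29] supplies the only control figures in the protocol, and no reference reporting endoscopic release is quantified.
- **The source cannot be checked.** What [29] itself counted as the event is visible only through the protocol's description.

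A reader might also infer three stronger things that the documents do not support.

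- **Rates of 38% and 82% at 4 and 8 weeks.** These arise from testing 55 lower GI patients alone, all with a stoma. The protocol describes one pooled primary analysis and gives patients without a stoma another event.
- **That the comparison measures only the interval and not the device.** Release still depends on healing, so a device effect would be mixed with the interval, not replaced by it.
- **That release is the wrong primary endpoint.** Section 5.2.1 defines wound healing as release, and relocation also depends on matters unrelated to healing. The fault lies in the pairing with the control.

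**Conclusion.** The point holds for lower GI patients with a stoma. Their event is release, the only control figures given are for completed relocation, and nothing in the protocol reconciles the two. The bias can run only towards the device.

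Its size depends on an assumed interval: from nominal (3%) if the two dates coincide to about 22% at 4 weeks and 55% at 8 weeks in the pooled test, or 15% and 38% if about 42 patients have a stoma. These figures also assume that [29] supplies the control curve, that the lag is constant, that observation lasts 3 months and that all other patients behave exactly as the control. The last is a convenience, since the protocol gives no control figure for release for oral intake. The need for correction rests on the definitions; the percentages show only what could be at stake.

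**What to change.** - **Sections 6.3.7 and 7:** keep release as the wound-healing endpoint, and state that it may be tested confirmatorily only against a reference that reports endoscopic release.
- **e-CRF and section 6.4:** add the date of actual stoma relocation, taken from routine records and also asked for in the final phone contact.
- **Any comparison of lower GI stoma patients with [29]:** use the relocation date as the event.

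**Cost.** One e-CRF field and wording changes. A reference reporting release has to be found, and its figures would replace 56% and 75% in planning for that endpoint. Where relocation is the event, fewer lower GI events fall inside the window: under the no-effect model with a 4-week lag, about 18.5 instead of 22.8 among 55 patients in 3 months. The comparison with [29] becomes less favourable to the device. The date should be added while sites are still documenting, because it may be hard to recover after database lock.

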6.1.5 Equipment to be used for assessing the study variables

Only data which are obtained in routine clinical care will be recorded and reported in the eCRF. Thus, no special equipment differing from routine clinical care will be used to assess the study variables.

6.1.6 Any procedures for the replacement of subjects

No study-specific intervention is defined within this observational study which is only following routine clinical care.

Patients' written informed consent to use and process their routine clinical care data according to data privacy standards will be obtained prior to documentation of any patients' data in the e-CRF. It is expected that in the majority of patients written informed consent to use and process data (enrolment) is provided after index therapy.

The principle for analysis of study data is intention to treat without restrictions to any subsequent course of follow-up.

Thus, no necessity of any procedures for the replacement of patients is foreseeable.

6.2 Investigational device(s) and comparator(s)

In this purely observational study no investigational devices will be used. However, a marketed medical device of interest will be used upon the investigator's decision according to medical guidelines and local policies. All medical devices used in this study are CE-marked, marketed devices which will only be used within the approved IFU in the intended patient population.

In this purely observational study without pre-defined therapy groups, no control group is defined, thus, no comparator devices are used.

Other medical devices which might be used reflect the medical decision of the investigator but are not defined or specified within the study protocol.

6.3 Subjects

About 110 adult female and male patients with acute defects, injuries and wounds in the oesophagus or rectum and an indication of treatment with Suprasorb[®] CNP endo system according to IFU and medical guidelines will be enrolled. Patients' written informed consent to use their routine clinical data according to data privacy standards must be obtained prior to documentation of patients' data in the e-CRF. All patients in whom the device has been used will be followed during routine clinical practice and will visit a site only in the course of their routine clinical care. No additional treatment or medical examinations will be performed.

It will be assured by means of the e-CRF system that treatments of upper GI tract and lower GI tract will be about equally balanced over the total study population.

6.3.1 Inclusion criteria

- **I1.** \geq 18 years of age
- **12.** Acute transmural defects, injuries and wounds in oesophagus or rectum, including perforations (iatrogenic or spontaneous) and anastomotic insufficiencies (Index defect)
- 13. Indication of treatment with Suprasorb[®] CNP endo system according to IFU and medical guidelines
- I4. Signed informed consent for usage of data

6.3.2 Exclusion criteria

- **E1.** Pre-existing coagulation disorders with increased risk of bleeding
- **E2.** Defects involving the bronchial system (bronchus/trachea/pulmo)
- E3. Any foreseeable deviation from IFU of Suprasorb® CNP endo
- **E4.** Known intolerance or allergy to one or more components of Suprasorb[®] CNP endo

6.3.3 Criteria and procedures for subject withdrawal or discontinuation

Patients enrolled into the study can withdraw consent for use of their data at any time for any reason without prejudice to further treatment or level of care. The investigator is not able to decide about the discontinuation of study participation of any patient. In the event that a patient withdraws consent, the date and reason for termination will be documented in the e-CRF according to ISO 14155:2020, section 7.10. In case of withdrawal of consent for use of data, no further data will be collected from the patient. The withdrawal of the informed consent shall not affect the use of data based on informed consent before its withdrawal. All reasonable efforts should be made to complete assessments and retrieve any outstanding data.

Due to observational nature of the study no specific procedures for follow-up of subjects following the end or a temporary or early termination of the study are defined. All medical care after withdrawal, discontinuation or regular end of the observation will be provided by the treating physician according to routine clinical care.

6.3.4 Point of enrolment (study sites)

About 10 study sites in Germany, which are trained for the use of Suprasorb[®] CNP endo system treatment in routine clinical care, will screen eligible patients.

Patients will be enrolled in this observational study if an indication for Suprasorb[®] CNP endo treatment was defined by the treating physician based on routine clinical care decisions, all inclusion and no exclusion criteria of the study are met and written consent is given to use and process their routine clinical data according to applicable data privacy standards.

It is expected that in the majority of patients written informed consent to use and process data is provided after routine clinical treatment of the index defect.

6.3.5 Total expected duration of the study.

The clinical phase of the study (first patient in to last patient out) is expected to last for 27 months with 24 months of enrolment and 3 months of follow-up of last patient in. After about 3 months of follow-up of the last patient treated with index therapy and subsequent final data cleaning, global end of study will be declared.

6.3.6 Expected duration of each subject's participation

The mean follow-up period (from date of enrolment to end of follow-up) of all patients is expected to be about 3 months.

6.3.7 Number of subjects required to be included in the study

As discussed in 3.2, the evidence for the different treatment options is very limited. Especially the patient populations, e.g. regarding underlying diseases, as well as the processes in the therapy are very different in the individual studies published. Therefore a reasonable sample size calculation is not possible at the moment. Thus, an interim analysis with sample size re-calculation is planned.

The best evidence for an **initial sample size calculation** is provided by data of the study by Wasmann et al. [29], a cohort study including 334 patients with ileal defects, where EVAC therapy was compared to conventional management of defect treatment. The median time to stoma relocation was estimated as 4 months in the EVAC group (interquartile range 3 to 6 months) versus 4 months (3 to 13 months) in the conventional management group. Therefore, the proportion of patients with stoma relocation after 6 months is known as 75% in the EVAC group. Assuming a constant increasing proportion in the conventional management group from 4 to 13 months with 2.8% per month, a proportion of 56% stoma relocations after 6 months is expected for the conventional group. Even if the follow-up is set to 3 months in this study, sample size calculation can be based on 6 months results.

Sample size calculation was performed with PASS 16.0.3 using a two-sided, one-sample log rank test. A group sequential design with the alpha spending function of O'Brien-Fleming results in a two-sided type one error of 4.92% for the final analysis. A sample size of 99 analysable subjects achieves 80% power to detect shorter time to release for food intake or endoscopic release for stoma relocation (assuming a proportion of relocated stoma of 75% after 6 months in the EVAC group when the proportion in the historic control group is 56%). The expected number of events during the study with 3 months of follow-up is 13. It is assumed that the survival time distributions of both groups are approximated reasonable well by the Weibull distribution with a shape parameter of 1.00. To account for treatment switching and early drop-outs of 10%, 110 analysable patients will be enrolled.

After data of complete follow-up of about half of the enrolled patients are available, an interim analysis will be performed and sample size will be recalculated. It is expected that until then the results of an ongoing randomized clinical trial comparing EVAC therapy to standard minimally invasive esophagectomy (refer to NCT04162860 and [22]) are available and can also be used as more reliable assumptions for sample size recalculation. The maximum sample size is set to 1.5 times the initial sample size, equal to 165 patients.

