In the study by Mees et al. [19] comparing patients treated with EVT (n=5: rectal carcinoma n=3, ulcerative colitis n=2) vs. transrectal lavage (n=5: rectal carcinoma n=3, ulcerative colitis n=2) after colorectal resection, median time of defect closure constituted 45 days in the EVT group, compared to 101 days in the lavage group. Average time in the hospital constituted 37 and 45 days, respectively. EVT was well tolerated by all patients and no specific side effects during or after the therapy were observed. One patient in the EVT group developed a mild rectal stenosis in the anastomotic area during the follow-up. This stenosis was treated by self-dilatation using Hegar's dilator for 4 weeks. Overall costs were summarized for both procedures considering the differences in the number of sessions (EVT - 7 replacements/ patient; lavage - 12 procedures/ patient), costs for staff and material. This resulted in comparable costs of $122.85 \in (EVT)$ vs. $119.4 \in (lavage)$, respectively.

Though a number of studies and case reports have demonstrated promising results regarding efficacy of EVT in treatment of both upper and lower GI tract perforations and anastomotic insufficiencies, and, potentially, even better safety profile of this treatment in comparison with other conventional treatment methods, the amount of data is still relatively small and additional data collection and analysis is necessary.

4. Benefits and risks of investigational device, clinical procedures and clinical study

All medical devices used in this study are CE-marked, marketed devices which will only be used in line with the approved IFU in the intended patient population.

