6.4.5 Follow-up (FU) visits

Every patient will be followed for 3 months after discharge after index treatment.

In line with routine clinical care, at least one personal follow up visit should take place within 3 months of follow up. To ensure comparability of data, in case this follow up visit has not been performed after 3 months (± 2 weeks) in addition a phone call with the patient should provide final information to be documented in the FU visit (phone) of the e-CRF.

At the FU visits the following data from clinical routine will be documented in the e-CRF (if available):

- Patient status
- Relevant concomitant medication and other treatment
- Safety related events: SAEs (including SADEs), AEs of special interest (including ADEs) and DD

Assessments*	Baseline visit	Index-Treatment	FU visits
Informed consent for data use	Х		
In- and Exclusion criteria	Х		
Demographic data	Х		
Medical history	Х		
Patient's status	Х		X**
Medication/other treatment	Х	X	X**
Concomitant diseases	Х		
Data regarding index treatment and related therapy		X	
Outcome of index treatment		X	
Safety related events (SAEs, SADEs, ADEs, DD)		X	Х

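### Three months of follow-up cannot rest on 6-month results: the protocol's own quartiles show no difference at months 3 and 4, so the stated 80% power does not hold for stoma release within the observed window

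*Protocol*

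**What the plan says.** Protocol 6.3.7 takes its planning figures from a cohort study of endoscopic vacuum closure (EVAC) versus conventional management: "The median time to stoma relocation was estimated as 4 months in the EVAC group (interquartile range 3 to 6 months) versus 4 months", with an interquartile range of 3 to 13 months in the conventional group. It reads 75% relocated at 6 months from the EVAC upper quartile. For the conventional group it draws a line from month 4 to month 13 at 2.8 points per month, which gives 56% at month 6. It then states: "Even if the follow-up is set to 3 months in this study, sample size calculation can be based on 6 months results".

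On method: "Sample size calculation was performed with PASS 16.0.3 using a two-sided, one-sample log rank test"; the group sequential design "results in a two-sided type one error of 4.92% for the final analysis". The resulting claim is: "A sample size of 99 analysable subjects achieves 80% power". Survival times are taken as Weibull with shape 1.00, that is, a constant hazard, and 13 events are expected with 3 months of follow-up.

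The observation period is described in three ways:
- Section 6.4.5: "Every patient will be followed for 3 months after discharge after index treatment".
- Section 6.3.5, on when the study is closed: "After about 3 months of follow-up of the last patient treated with index therapy and subsequent final data cleaning, global end of study will be" (sentence cut short here).
- Section 6.3.6: a mean of about 3 months, counted from enrolment.

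The endpoint clock starts at the index treatment (6.1.3.1, 6.4.1). Section 7 calls the superiority test confirmatory, and 6.3 plans about equal numbers of upper and lower GI patients.

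**The concern.** A 6-month contrast can stand in for a 3-month one only if the groups already differ early and in the proportion that the model assumes. The quartiles in the same paragraph say otherwise: the lower quartile and the median are equal, and only the upper quartile differs. Even the 56% is built on a line that leaves the common median at month 4. The effect that powers the study therefore lies late, while observation stops at or soon after the point where the quoted figures begin to differ.

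At stake is the meaning of a confirmatory test for about half the patients. If the device performs as in the reference cohort, a non-significant lower GI result could reflect the length of the window as easily as a lack of effect. The interim recalculation does not repair this: it can raise the number of patients to 165 but does not lengthen follow-up.

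**Working it through.** **Inputs.** Protocol 6.3.7: quartiles 3/4/6 and 3/4/13 months; 75% versus 56% at month 6; two-sided 4.92%; 99 analysable patients; one-sample log-rank test; shape 1.00. Section 6.4.5: 3 months after discharge. Section 3.2, from a series of 5 versus 5 patients after colorectal resection: "Average time in the hospital constituted 37 and 45 days, respectively" for vacuum therapy and lavage.

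**1. The plan's own figure.** The formula is n = (z₁₋α/₂·√E₁[Λ₀] + z_power·σ₁)² / (E₁[δ] − E₁[Λ₀])², with constant hazards and censoring at 3 months. Entering 75% and 56% as *event-free* proportions gives E₁[δ] = 1 − √0.75 = 0.134, E₁[Λ₀] = 0.270 and σ₁ = 0.392. Then n = (1.967 × 0.520 + 0.842 × 0.392)² / 0.136² ≈ 99, with 99 × 0.134 = 13.3 events. Both stated figures reproduce at a 3-month window, but only with the proportions turned round. Entered as the text defines them (proportions *relocated*), 99 patients give 99 × (1 − √0.25) = 49.5 events, and the required number is about 56 to 74 depending on the variance formula. That inversion is a separate error. Here it shows that the 80% comes from a constant-hazard model at 3 months.

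**2. What constant hazard implies, against the quartiles.**
- Relocated at month 3: EVAC 1 − 0.25^(3/6) = 50%; conventional 1 − 0.44^(3/6) = 34%. Quartiles: 25% and 25%.
- Median: EVAC 6·ln 2/(−ln 0.25) = 3.0 months; conventional 6·ln 2/(−ln 0.44) = 5.1 months. Quoted medians: 4 and 4.

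The model has an early effect that the quoted figures do not show.

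**3. The window from index use.** 3 + 37/30.4 = 4.2 months; 3 + 45/30.4 = 4.5 months. A 60-day stay (assumed) gives 5.0. Reaching month 6 needs a stay of about 3 months.

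**4. Power on the quartile curves.** Straight lines join the quartiles, as the protocol itself does for the conventional group. From month 4, EVAC rises by 12.5 points per month and conventional by 2.8. The test is simulated as Z = (O − E)/√E, 20,000 runs, n = 99, reference curve taken as known; power is in the favourable direction.

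| Window (months) | EVAC vs conventional | O | E | Power |
|---|---|---|---|---|
| 3.0 | 25% vs 25% | 24.7 | 24.7 | 3% |
| 4.2 | 53% vs 51% | 52.2 | 50.1 | 5–6% |
| 4.5 | 56% vs 51% | 55.4 | 50.8 | 10% |
| 5.0 | 62% vs 53% | 61.5 | 51.9 | 26% |
| 6.0 | 75% vs 56% | 74.2 | 53.8 | 82% |

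The 3% at month 3 is the one-tail false-positive rate. With about 50 lower GI patients, power is 5 to 8% at 4.5 months and 43 to 51% at 6 months.

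**5. Sensitivity.**
- Release 0.5 to 1 month before relocation in both groups, which acts like a window longer by that amount: about 17 to 39% at 4.2 months, and about 26 to 53% at 4.5.
- Rounding in the device's favour, with true quartiles of 2.8/3.8 versus 3.2/4.2: about 28% at 4.2 months.
- Near the rounding limit, 2.6/3.6 versus 3.4/4.4: about 77 to 79%.

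**The case against.** **The endpoint is endoscopic release, not relocation.** Release may come earlier. This stands as a limit on the figures. The protocol equates the two in its calculation and states no lag; a common shift of up to a month leaves power at about 39% (4.2 months) or 53% (4.5 months). If only the device series counted release while the reference stayed on relocation, the test would reject about 54% (half a month) to 95% (one month) of the time at 4.2 months. Those rejections would reflect mismatched events, not benefit. For the same reason, a reader who infers that the study is bound to see almost no difference goes further than the documents allow.

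**Other cited series show earlier healing.** Section 3.2 also reports closure at a median of 45 versus 101 days in that 5 versus 5 series, and 40.5 days in 14 patients. Both fall inside the window. So it cannot be said that all published data place the effect after the last contact; but these are not the data on which the sample size rests.

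**Whole-month quartiles do not prove identical curves.** Correct. They show agreement at two points only. Power near 80% at 4.2 months, however, needs rounding of about 0.4 month, in opposite directions in the two groups, at both quartiles.

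**The assumptions are provisional.** Section 6.3.7 says so and plans a recalculation. That excuses uncertain inputs, not a bridging statement that the adjacent figures contradict.

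**Conclusion.** The bridging sentence in 6.3.7 is wrong as written, and the 80% power is not supported for stoma release within the observed window. On the protocol's own quartiles, power with 99 patients is about 3% at 3 months, 6 to 10% at 4.2 to 4.5 months and 26% at 5 months. This assumes straight lines between quartiles, release treated as relocation, a known reference curve, and a hospital stay taken from a very small series. The plausible departures in step 5 raise power but leave it well short of 80%; only rounding near its limit comes close.

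Three further inferences are tempting and do not hold:
- That most lower GI patients would be censored before release. At 4.2 months the EVAC curve already stands at 53%.
- That the stated 80% was derived from 6 months of observation. N = 99 and 13 events reproduce at 3 months; the 82% found at 6 months on the quartile curves is a coincidence.
- That a 6-month contact alone restores 80% for lower GI patients. With about 50 of them it gives about 51%.

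The point is confined to lower GI use with a stoma, because the protocol gives no control curve for oral food intake.

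**What to change.** **Needed.** In 6.3.7, delete the sentence that 6-month results can serve for 3 months of follow-up. State that the 80% power does not hold for stoma release within the observed window, and recompute it from quartile-based curves at the actual window, with the release-to-relocation lag as a stated assumption. Reconcile the start of the 3 months: index therapy in 6.3.5, enrolment in 6.3.6, discharge in 6.4.5. This costs wording and one recalculation.

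**Preferred in addition.** In 6.4.5, for lower GI patients with a stoma, add one phone or record contact at 6 months after index use to capture the date of release, and align 6.3.5, 6.3.6 and Annex 2. This takes a protocol amendment and one contact for at most about half the patients, and the last contact moves about 2 to 3 months later. It adds no patients and no procedures, and 6.4.5 already provides for a phone call. Because power for that half would still be only about 51%, report the lower GI result as an estimate with its confidence interval and do not present the extension as restoring 80%.
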